Using Augmented Reality to 3D Map Needle Pathways in Real Time to Enhance Neuraxial Anesthesia

Co-Principal Investigators:

[name] (MD, FRCPC, MHSc)

[name] (MD, FRCPC)

Co-Investigators:

[name] [name] [name] [name] Au [name]

Background:

Neuraxial anesthesia (spinal and epidural) has traditionally been a 'blind' technique. The subarachnoid or epidural space is identified via anatomical landmarks, relying on operators' feel and skill, both are subjective, lack complete accuracy and highly influenced by patient body habitus where obese patients or those with anatomical variations, or spinal abnormalities are shown to be quite challenging^{1,2}. Neuraxial anesthesia is not a benign procedure as multiple attempts or inaccurate trajectories of the needle can not only be anxiety provoking and cause patient discomfort but can also lead to patient morbidity in the form of spinal/epidural hematomas, infection, dural puncture headaches and nerve injury³.

The use of ultrasound (US) has become routine for peripheral nerve blocks as it allows for real-time views of needle position for peripheral blocks to achieve higher rates of success, fewer complications, reduced patient discomfort, and quicker procedural times⁴. The needle and/or target structures are kept in constant view with the use of ultrasound during the block procedure to allow for higher accuracy. As such, US guidance has become the *de facto* standard of care for peripheral nerve blocks and in fact, is now mandated by the Royal College of Physicians of the United Kingdom for central line insertion⁵.

Though increasing in popularity, US guidance for neuraxial procedures is still relatively uncommon due to technical challenges of real-time guidance in conjunction with the difficulties of US imaging of bony structure⁶. However, different from US-guided peripheral nerve blocks, the common technique for US use in neuraxial anesthesia is to provide *pre-procedure* landmarks so the operator has an accurate prediction for the placement of the needle tip, depth and trajectory before actual needle insertion. Anatomical landmarks are visualized using the US along multiple viewing planes and skin markings are made based on these images. The US probe is then placed at rest and subsequent needle insertion is done in a semi-blind manner based on the skin markings and knowledge of approximate depth and trajectory from memory.

Multiple reviews have been published recently detailing the procedure of US-guided spinal and epidural anesthesia at the lumbar spine, though not in real time^{6,7}. They have shown that US reduces procedure time, number of needle passes, needle contact with bone, and other complications compared to traditional placement techniques based on operator feel^{7,8}. Despite this, the process of placing the US probe at rest and then moving forward with the procedure based on skin markings has the downfall of trying to imitate accurate needle trajectory beneath the skin based on the operator's memory⁹. This may also lead to multiple attempts at needle placement or failure of the procedure, challenges that are important to consider when attempting thoracic spine neuraxial techniques. Notably, due to the steep angulation of the spinous processes at the thoracic level, achieving needle trajectory to get to the epidural space can prove to be quite challenging¹⁰.

In contrast to lumbar epidurals where a midline approach is used, the common technique for thoracic epidurals is a 'paramedian' approach. This involves purposely contacting lamina with the needle and continuously adjusting in a cephalad/midline direction to ensure that the operator is walking up the bone until the epidural space is entered. The paramedian approach mitigates having to navigate the difficult bony landmarks at the thoracic level. However, hitting bone with the needle can cause patient discomfort. While US landmarks can be done with thoracic epidurals, the needle trajectory is of greater difficulty to predict if the insertion is made solely on memory from the US images. Hence, US is yet to be commonly adopted as an approach for thoracic epidurals unlike lumbar spine neuraxial techniques.

To address the problem, we propose to use augmented reality technology as a tool to provide a superimposed US image as an *objective* alternative to the operator's memory. Microsoft HoloLens is a head mounted augmented reality device, which allows for overlaying computer-generated elements to the real

world. Notably, this technology presents a unique opportunity where we will be able to combine the US image and angulation of the US probe to instantly create, in real time, spatially stable holograms overlaying the patient's anatomy in the user's field of view. Thus, when the operator locates the anatomical landmarks using an US for a neuraxial technique, a holographic needle trajectory can be instantaneously generated and remains on the patient even after the US probe is placed at rest.

The model we propose in this project is truly innovative in medical content and involves a partnership with software and engineering experts. In collaboration with our partners, we have recently designed and developed the first model of a live holographic anatomical marking system using Microsoft HoloLens. We aim to pilot the prototype on a three-dimensional (3D) printed see-through thoracic spine phantom by four experienced staff regional-anesthesiologists to determine the accuracy of the holographic trajectory. We strongly believe, that using augmented reality, it will be possible to provide an accurate *live* road map for the needle path hidden under the patient's skin. Also, this alongside 3D object recognition will bring in a variety of potential uses in anaesthesiology.

Overall Aims and Objectives:

Our goal is to combine academic, medicinal and industrial expertise in a partnership to create a new technique for use in medicine. This partnership will strengthen the important area of human health, neuraxial anesthesia, and ultimately, will better facilitate the translation of research discoveries into applied therapies.

The objectives of this study are to assess whether the use of augmented reality in the form of creating a holographic marking of the site of needle insertion and optimal angulation will 1) reduce procedure time by increasing first past success when used as a guide to the thoracic epidural space, and 2) increase needle accuracy when compared to traditional ultrasound landmark-based techniques.

Hypothesis:

We hypothesize that using augmented reality through HoloLens, the creation of a newly developed holographic tool for neuraxial anesthetic techniques will increase needle accuracy thereby decreasing procedure time.

Methodology, Experimental Design and Evaluation

The 3D Phantom model. A thoracic spine ultrasound phantom (Figure 1) was constructed utilizing open source BodyParts3D library anatomy files. This library was created based on whole body MRI images with 2mm slice thickness of a healthy male volunteer¹¹. A container and associated parts were designed and 3D printed using AutoDesk Fusion 360 and a Creality CR-10S from PLA, respectively. When filled with compatible gel and covered with a layer of surgical glove material (to obscure the location of the spine with the opaque gel¹²), the model has interlaminar acoustic windows and depth characteristics compatible with population averages when viewed with a portable ultrasound¹³. The phantom has similar palpation characteristics to a patient, and a standard loss of resistance to saline occurs on entrance of a needle to the spinal canal cavity.

[figure not shown]

Figure 1: 3D Model of Thoracic Spine Ultrasound Phantom

Study design and workflow.

Local research ethics approval will be sought prior to study participant's recruitment. Only participants who meet inclusion/exclusion criteria (Table 1) will be approached for participation in this study.

We aim to study 84 sequential thoracic epidural events and randomize them to one of two study groups: Group 1, landmark based thoracic epidural technique (control) or, Group 2, HoloLens-assisted thoracic epidural technique (intervention). Sunnybrook Health Sciences has a dedicated regional block room and four experienced regional anesthetists that are trained and experienced in the thoracic epidural technique and will perform thoracic epidurals for this study (see Table 1 for inclusion criteria). Prior to the start of the study, the four expert anesthesiologists will practice needle insertion on the above described phantom model by attempting needle insertion 20 times each, or until they felt comfortable with the system, while wearing the Microsoft HoloLens. The anesthesiologist performing the thoracic epidural insertion procedure will be randomized to either study Group 1, or 2. In Group 1 (control), the staff anesthesiologist will follow the traditional technique for US-guided thoracic epidural insertion. Briefly, the anesthesiologist will use the US to identify and mark the appropriate spot for placement of the thoracic epidural catheter. The US probe is then placed at rest and the anesthesiologist will proceed with thoracic epidural needle insertion following standard techniques.

In Group 2 (intervention), the staff anesthesiologist will use the HoloLens tool to assist with the traditional technique as described above for Group 1. In combination with the US, a hologram image of the trajectory towards the epidural space will be generated, thereby mitigating the need to walk off the lamina. The holographic system will mark the appropriate spot for placement of the thoracic epidural catheter. Then, the needle will be inserted following the holographic trajectory overlaid on the patient's back. The hand movements and realtime ultrasound images of the small portion of the patient's spine with no visually identifying features will be recorded during procedure. The anesthesiologists' hands and needle movement will be captured and will be used post-procedure as a back-up to real-time assessments by anesthesiologists and research assistants to confirm the procedure time and needle movements. The recordings and ultrasound images will be stored in a de-identified manner.

Inclusion Criteria:	Exclusion Criteria:
Anesthetists	Patients
 Trained in US-guided epidural technique with fellowship Performed >100 thoracic US-guided epidural procedures 	 Age <18 Lack of verbal patient assent after study introduction

Table 1. HoloLens study participants inclusion and exclusion criteria.

Sample Size Calculation and Statistical analysis:

A previous published studies have revealed that mean thoracic epidural catheter placement using traditional palpation and landmark guidance requires 10 minutes with a standard deviation of 3 min^{14,15}. Therefore, having 2 minutes reduction in procedure time (i.e. 20% relative reduction) will be considered a meaningful in the context of patient comfort and operating room efficiency. Considering a 2-sided type I error rate of 5% and power of 80%, 36 participants will be required per group, and 72 participants will be required to complete the study. Assuming possible participants withdrawal from the study, we will recruit 84 study subjects to compensate for an expected 15% withdrawal rate. Each of the four anesthesiologists will complete an equal number of thoracic epidurals.

Secondary outcomes that are continuous in nature (e.g. number of skin punctures, number of needle movements, procedural pain score) will be analyzed in the same manner. For binary outcomes (parasthesias, dural puncture, PCA in PACU) the Chi square test (or Fisher's exact when expected cell counts are less than 5) will be utilized. To account for multiple comparisons, we will use the Holm-Bonferroni method and an adjusted p<0.05 will be considered significant.

Expected Outcomes measures:

To address our specific objectives of whether the HoloLens tool and methodology, that is designed to allow a holographic marking of the needle insertion site and optimal angulation would 1) decrease procedure time by increasing first past success when used as a guide to the thoracic epidural space; and 2) increase needle accuracy when compared to traditional ultrasound landmark based techniques, we will ask an observer (i.e. anesthesiologist) to document following:

- A. the time to procedure completion starting from skin puncture to time at which the Tuohy needle is withdrawn;
- B. the number of needle movements (in any direction/re-direction);
- C. number of skin punctures made;
- D. patients' pain score during the procedure using the numeric rating scale (NRS);
- E. any complications during the procedure such as paresthesias, dural punctures;
- F. the need for patient controlled analgesia (PCA) in PACU (constituting failure of epidural).

Lastly, the patient will be asked to rate their level of overall discomfort during the procedure on a scale of 0-10 (0 - being no pain/no discomfort and 10 being worst possible pain/extreme discomfort) at its conclusion. Similarly, the regional anesthesiologists will be given a questionnaire regarding ease of use and limitations of the technique. Our survey strategy will help to validate study results, and enable optimization and implementation of the novel technology.

Knowledge Translation

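### The plan names two units of randomization, the epidural event and the anesthesiologist; the second statement should be reworded, and the undescribed primary analysis should be stated with an operator term

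*Combined protocol and SAP*

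**What the plan says.** The unit of randomization is given twice in the same paragraph of 'Study design and workflow'. The first statement is "We aim to study 84 sequential thoracic epidural events and randomize them to one of two study groups". The second, a few sentences later, is "The anesthesiologist performing the thoracic epidural insertion procedure will be randomized to either study Group 1, or 2".

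Other statements bear on which is meant:
- Before the trial, "the four expert anesthesiologists will practice needle insertion on the above described phantom model" while wearing the headset. This applies to all four.
- 'Sample Size Calculation and Statistical analysis' counts participants, 36 per group and 72 in total, and adds that "we will recruit 84 study subjects to compensate for an expected 15% withdrawal rate". It has no term for clustering by operator.
- 'Expected Outcomes measures' says that "the regional anesthesiologists will be given a questionnaire regarding ease of use and limitations of the technique".
- The sample size section ends with "Each of the four anesthesiologists will complete an equal number of thoracic epidurals". This fixes totals per operator, not the split between arms within an operator.

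On analysis, the binary outcomes get a chi-square or Fisher's exact test. The continuous secondary outcomes are referred back to a method that does not appear in the available text. Operator is not mentioned in any described analysis, and no stratification or blocking by operator is described.

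**The concern.** A trial that randomizes events, with each operator working in both arms, and a trial that randomizes four operators need different sample sizes and different analyses. The stated numbers fit only the first. Someone preparing the allocation list from the second sentence alone could run the other trial, in which the difference between arms cannot be separated from the difference between two pairs of operators.

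The second matter is precision. Operator is known before every case, and the Background describes the control technique as "trying to imitate accurate needle trajectory beneath the skin based on the operator's memory", so some variation between operators is plausible. Under per-event allocation that variation causes no bias, but it adds noise that an operator term could remove.

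**Working it through.** **Inputs from the plan.** Control mean 10 min, SD 3 min, difference 2 min, two-sided alpha 5%, power 80%, 36 per group, 84 recruited, four operators with equal totals (84/4 = 21 recruited and 72/4 = 18 completing per operator).

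**Assumptions.** The documents give no between-operator variance, so the ICC is varied. SD 3 is taken as the total SD, including operator variation.

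**1. The plan's own figure.** n per group = 2 × [3 × (1.960 + 0.842)/2]² = 35.3, so 36, as stated. Power at 36 per group is 80.7% by normal approximation and 79.7% by t-test. For withdrawals, 72/0.85 = 84.7 and 72 × 1.15 = 82.8; the stated 84 lies between them. The calculation treats participants as independent, as per-event allocation allows.

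**2. Operators randomized, two per arm, 18 completers each.** Design effect = 1 + 17 × ICC. The standard error without clustering is 3 × √(2/36) = 0.707 min.

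| Assumed ICC | 0.05 | 0.10 |
|---|---|---|
| Design effect | 1.85 | 2.70 |
| Effective n per group, 36/design effect | 19.5 | 13.3 |
| Standard error, 0.707 × √(design effect), min | 0.96 | 1.16 |
| Power, normal approximation | 55% | 41% |
| Power, t-test on operator means (2 df) | 23% | 18% |
| Type I error if operator is ignored, 2 × [1 − Φ(1.96/√(design effect))] | 15% | 23% |

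Simulation gives about 15% and 24% for the last row.

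**3. Events randomized.** Simulation of 60,000 trials per cell, 4 × 21 events, 72 of 84 retained at random. The unadjusted test has 70 df and the model with operator 67 df.

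| Assumed ICC | 0 | 0.05 | 0.10 | 0.20 |
|---|---|---|---|---|
| Not stratified, no operator term: type I error (%) | 5.0 | 4.8 | 5.0 | 5.0 |
| Not stratified, no operator term: power (%) | 79.5 | 80.1 | 80.7 | 81.3 |
| Not stratified, operator term: power (%) | 77.7 | 79.9 | 82.2 | 86.0 |
| Change from the term alone (points) | −1.8 | −0.2 | +1.5 | +4.7 |
| Stratified, operator term: type I error (%) | 4.9 | 5.1 | 5.0 | 5.1 |
| Stratified, operator term: power (%) | 79.2 | 81.2 | 83.1 | 87.4 |

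Repeat simulations put the power of the term alone at ICC 0.20 between 84% and 86%, so the gain there is best read as 3 to 5 points. Type I error with the term and no stratification was 5.2, 4.7, 5.2 and 5.0% in a run of 10,000 trials per cell. Stratification adds 0.8 to 1.5 points to the term alone. Stratified allocation analysed without the term is conservative, with type I error about 3.6-3.8% at ICC 0.20.

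**4. Predictability.** An unblinded operator who guesses the arm seen less often among his own cases is right about 51% of the time with one central 42:42 list, 59% with a single random ordering of 21 per operator, and 67-68% with operator lists in small varying blocks.

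**The case against.** The second sentence has an innocent reading: the operator doing a given case is told which technique to use for that case. That is per-event allocation in loose words, and it is probably what was meant. This stands, and it is why the first fix is one of wording. A reader might infer from the sentence that this is a four-cluster trial with inflated type I error. The documents do not support that, given headset practice by all four operators and a participant-based sample size. The inference is strong but still an inference. The equal-workload sentence does not help settle it, since two operators with 21 cases each would also give 42 per arm.

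On the operator term, three objections carry weight. First, the primary analysis is missing from the available text, so an operator term in it can be neither confirmed nor excluded. A reader might infer that the plan discards available precision; all that can be said is that no described analysis uses operator. Second, the term alone loses about 2 points at ICC 0 and gains nothing at 0.05. Table 1 requires fellowship training and "Performed >100 thoracic US-guided epidural procedures", which should narrow operator differences, and the Background's remark on memory describes a limit of the technique, not a measured spread between operators. Third, stratified lists make allocation easier to guess for operators who cannot be blinded to a headset. The 51% comparator also assumes that each operator follows only his own cases; one who tracked all 84 would be right about 56% of the time. These points make stratification a trade-off rather than a recommendation.

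It is also tempting to extend the operator term to the secondary and binary outcomes. Every calculation here concerns procedure time, so no benefit has been shown there, and splitting sparse events over four operators could lose information.

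**Conclusion.** The contradiction in the unit of randomization is real and needs no assumption to establish. The intended per-event design is valid: no bias, type I error near 5%, power close to the stated 80%. Following the second sentence literally would deliver neither the stated power nor the stated error rate; the size of that failure rests on the assumed ICC of 0.05 to 0.10 and on two operators per arm.

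The operator term is a cheap improvement, not the repair of a defect. Its effect runs from a loss of about 2 points to a gain of 3 to 5 over the assumed ICC range, with break-even slightly above 0.05. Nothing in the documents locates this trial within that range.

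**What to change.** 1. Replace the second statement of the unit with: *Each epidural event will be randomized 1:1 to Group 1 or Group 2.* The cost is one sentence.
2. State the primary analysis as a linear model of procedure time on arm, with anesthesiologist as a fixed effect. The cost is 3 degrees of freedom and, if the operators do not differ, about 2 points of power. No extra patients, visits or staff are needed.
3. Optional: stratify allocation by anesthesiologist. It adds about 1 to 1.5 points and removes most of the loss at ICC 0, but needs four lists instead of one and makes allocation easier to guess. Because 21 is odd, two lists would end 11:10 and two 10:11 to keep 42:42. If stratification is used, the operator term must be kept, since the plain test becomes conservative. Record the decision either way.

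The tests for secondary and binary outcomes can stay as they are on this point.

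### Patients are not masked to their arm, and whoever collects pain and discomfort is not said to be independent of the operator, so a benefit on these secondary ratings could not be separated from expectation

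*Combined protocol and SAP*

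**What the plan says.** The two arms are "Group 1, landmark based thoracic epidural technique (control) or, Group 2, HoloLens-assisted thoracic epidural technique (intervention") (Study design and workflow). Both use ultrasound and marking. In Group 2 the HoloLens is added, and "the needle will be inserted following the holographic trajectory overlaid on the patient's back". The Background places the holograms in the field of view of the person wearing the headset.

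Under Expected Outcomes measures, "we will ask an observer (i.e. anesthesiologist) to document following" introduces items A to F. Item D is "patients' pain score during the procedure using the numeric rating scale (NRS"). Discomfort comes after that list: "Lastly, the patient will be asked to rate their level of overall discomfort during the procedure on a scale of 0-10", at the end of the procedure. No recorder is named for it.

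The analysis section treats pain as a tested secondary outcome ("Secondary outcomes that are continuous in nature (e.g. number of skin punctures, number of needle movements, procedural pain score) will be analyzed in the same" …). For multiplicity, "we will use the Holm-Bonferroni method and an adjusted p<0.05 will be considered significant". Discomfort appears in neither the continuous nor the binary list of analysed outcomes.

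The video recording serves as "a back-up to real-time assessments by anesthesiologists and research assistants to confirm the procedure time and needle movements". It does not cover pain or discomfort. No section mentions blinding or masking of patient, operator or observer. Table 1 refers to a study introduction before verbal assent but does not give its content.

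**The concern.** Both ratings are self-reports given during or just after the procedure. A patient who knows that the new device was used may rate pain lower, and may do so more readily if the person asking took part in the procedure. Procedure time and needle movements can be checked afterwards on video. A pain score cannot, so any protection has to be in place when the score is collected.

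Patient comfort is one of the two reasons the plan gives for calling a 2-minute saving meaningful, and the plan says its survey strategy will help validate the results. These ratings will therefore be read as evidence for the device. If they favour the HoloLens, the trial as written gives no means of telling less pain from a kinder report.

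**Working it through.** **The plan's own figure.** The sample size rests on procedure time: difference 2 min, SD 3 min, two-sided 5%, power 80% (Sample Size Calculation and Statistical analysis). n per group = 2(1.960 + 0.842)² × 3² / 2² = 35.3, rounded up to 36, so 72 in total. This reproduces. Allowing for 15% withdrawal, 72 / 0.85 = 84.7, or 85 against the stated 84, an immaterial difference. None of these inputs depends on patient reporting.

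**Illustration for the pain score.** Inputs:
- From the plan: n = 36 per arm, two-sided 5%, Holm-Bonferroni.
- Assumed, because the documents give no values: SD 2 to 3 on the 0-10 scale; an expectation shift b of 0.5 or 1 point favouring the HoloLens; true effect zero; a two-sample t-test.
- Assumed size of the Holm family: 7 tests (procedure time, needle movements, skin punctures, pain, paresthesias, dural puncture, PCA). The plan does not state the family.

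The test statistic is noncentral t with 70 degrees of freedom and noncentrality (b / SD) × √(36/2). The critical value is 1.994 at 0.05, and 2.771 at the strictest Holm step, 0.05 / 7 = 0.0071. For b = 1 and SD = 2, the noncentrality is 0.5 × 4.243 = 2.121.

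| Shift (points) | SD | Unadjusted | Strictest Holm step |
|---|---|---|---|
| 0 | any | 5% | 0.7% |
| 0.5 | 2 | 18% | 5% |
| 0.5 | 2.5 | 13% | 3% |
| 0.5 | 3 | 11% | 2% |
| 1 | 2 | 55% | 27% |
| 1 | 2.5 | 39% | 15% |
| 1 | 3 | 29% | 9.5% |

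Under Holm, a p-value at or below 0.05/7 is always rejected and one above 0.05 never is. The chance that pain is declared significant therefore lies between the two columns, depending on the other outcomes.

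A larger sample makes this worse, because the bias stays while the standard error shrinks. With all 84 enrolled patients (42 per arm), a 1-point shift gives 33% to 62% unadjusted and 12% to 33% at the strictest Holm step.

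**Is masking plausible?** The documents describe the same ultrasound-based technique in both arms, work on the patient's back, and a hologram in the wearer's field of view. That makes masking plausible but does not establish it. Patient position, when the headset goes on, and what is said aloud are not described.

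**The case against.** The strongest reply is that much of the worry is read into silence, and part of that reply stands.

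- A reader might infer that this is an open trial in which patients are told their arm. The documents do not say so. They support only that no masking is provided for.
- A reader might infer that the operator, or an anesthesiologist in every case, records both ratings. The text names an observer for items A to F, which reads more naturally as someone other than the operator, and names nobody for discomfort. What stands is that independence from the operator is not stated.
- Masking might fail. The headset is worn on the head, set-up or conversation could reveal it, and the plan expects the needle technique itself to differ between arms.
- Research assistants appear only in the Group 2 description, in connection with time and needle movements. Their presence in Group 1 is not stated, and an assistant at the bedside would see the headset.
- A reader might extend the point to PCA in PACU. The documents do not say who decides on PCA, on what basis, or whether those staff know the arm, so that extension is not supported.
- Quoting only unadjusted rates would overstate the size, since the plan applies Holm. Both are therefore shown.

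None of this removes the central point. The plan tests a self-reported pain score without saying what the patient knows or who asks. Multiplicity adjustment lowers the chance of a false claim but does not correct bias.

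**Conclusion.** The point holds for procedural NRS pain and the discomfort rating, and only for these. As written, the plan could not separate an apparent benefit on them from expectation. At a 1-point shift, the chance of a significant pain result with no true effect is 29% to 55% unadjusted and about 9.5% to 27% at the strictest Holm step, against 5% and about 0.7% without bias. The SD, the shift and the 7-test family are all assumptions, so these figures show how sensitive the outcome is and do not predict the bias. A reader might infer that the trial's main result is compromised. The documents do not support that on this ground: procedure time does not come from patient report, and the sample size is unaffected. This is a cheap improvement to secondary outcomes that cannot be made once the ratings have been collected.

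**What to change.** State in the protocol and in the consent script that:
- patients agree to either technique and are not told their allocation until pain and discomfort have been rated;
- the arm is not announced, and the headset is put on out of the patient's sight where feasible;
- a non-operator, such as a study research assistant used in both arms, asks for both ratings from a fixed script.

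If masking proves impracticable, say so and report both ratings as unblinded.

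The cost is mainly wording. Sample size, alpha and power do not change. Whether a research assistant is already present for Group 1 procedures must be confirmed. If not, that attendance is an added cost. Two limits remain: some patients may guess their arm, and a rater who sees the headset is independent of the operator but not blinded.
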